2.3 RISK/BENEFIT ASSESSMENT

2.3.1 KNOWN POTENTIAL RISKS

Aim1: Potential loss of privacy and/or confidentiality is the main potential risk to subjects associated with this portion of the study. This risk will be minimized by following Northwell's Protected Health Information (PHI) protocol that includes storing data in Research Electronic Data Capture (REDCap), or within a locked electronic folder on a secure, HIPPA-compliant, institutional server. Data received from the WTC Data Center will be uploaded into the password-protected REDCap database. Only designated research study staff will have access to the study database, to further minimize risk. At the start of the focus group, participants will be reminded about confidentiality and how it is important not to discuss the focus group content outside of the focus group. Only first names (or pseudonyms if preferable) will be used during the focus group. To minimize the potential impacts of discussing sensitive topics, a psychologist with qualitative research and a mental health care background will oversee qualitative data collection. The focus group will also occur at the site of the Queens WTCHP so that direct referrals to on-site WTC mental health staff can be made if necessary. The audio recordings will be stored in a password-protected file on the FIMR at Northwell Health's (NWH)s secure network, and deleted from the audio recorder. Recording transcripts will be stored in a locked

Protocol Number: 21-0640

February 1, 2022

electronic folder on a secure, HIPAA-compliant, institutional server. If done remotely due to COVID-19 restrictions, only a Northwell approved platform will be used.

Aim 2: Study Assessments

There are no major risks around assessments. Potential loss of privacy and/or confidentiality is one potential risk to subjects associated with this portion of the study. As stated above this risk will be minimized by following Northwell's PHI protocol that includes storing data in REDCap, or a locked electronic folder on a secure HIPAA-compliant institutional server. Only designated study staff will have access to the study database and locked electronic folder, to further minimize risk. A unique identifying number will be assigned to each subject at the time of randomization in order to safeguard the subjects' PHI. Only the project coordinator will have access to the password-protected REDCap file that links the random identification number to the subject information.

There is a risk that some of the questions involved in the assessments could cause potential stress or discomfort. The investigative team will vigilantly observe each participant's emotional reactions during all study procedures, and offer referrals when appropriate. If the mental health symptoms of any participant were to worsen, [name] would be responsible for assessing and referring for treatment within the WTC Health Program. Given the exclusion criteria (no signs of psychosis, mania, bipolar disorder, active substance dependence, or suicidal/homicidal intent) we hope to limit the likelihood of adverse events regarding mental health symptoms.

Aim 2: taVNS

The taVNS device is Nesos MAUI PROTECT System— a wearable, external stimulator that generates electrical pulses transcutaneously delivered to the auricular branch of the vagus nerve through the ear canal. The type of stimulation (including shape, frequency, pulse width, amplitude, total charge, and energy delivered to the subject) is comparable to the levels applied by commercially available transcutaneous electrical nerve stimulation (TENS) stimulators. The Nesos MAUI PROTECT System is a type of TENS, classified as non-significant risk by the FDA and does not require an IDE.

Although highly unlikely, for participants with any severe or persistently worsening symptoms or adverse reactions, the taVNS therapy will be immediately discontinued, they will be removed from the study, considered treatment failures, and receive medical treatment as necessary. Participants will be taught safe practice with the use of a taVNS unit, such as checking and cleaning skin before starting a session, monitoring skin for signs of irritation, securing electrodes with even pressure distribution and full contact, and watching for signs of unit malfunction requiring maintenance.

Protocol Number: 21-0640

February 1, 2022

The patient manual also provides details for participants regarding the following risks and they are asked to contact their provider and site coordinator if any occur:

The Nesos System exhibits a safety profile similar to that of commercially available TENS units. Possible, but rare, side effects may include:

- Bradycardia
- Skin erosion at electrode site
- Pressure sores
- Unbearable pain at the electrode site
- Undesirable sensation at electrode site
- Uncomfortable stimulation of tissue around the electrodes
- Uncomfortable heating effects, discomfort or burn
- Intermittent stimulation
- Tingling, prickling or numbness
- Tissue reaction to stimulation
- Tissue reaction or allergy to materials
- External sources of electromagnetic interference that cause the device to malfunction
- Failure of device components including breakage, hardware malfunctions, loose connections, electrical shorts or open circuits and insulation breaches
- Failure or malfunction requiring discontinuation of use

Although the Nesos device delivers transcutaneous electrical stimulation, to date, there are no FDA cleared devices that use the auricular nerve of the vagus on the external ear to deliver stimulation therapy in the manner that we do. Based on safety data collected from all of the studies using the same device representing more than 200 patients and over 2500 hours of stimulation, including data from 15 patients who used the device for 12 months (daily). Nesos states they have also not had any reports of SAE or UADEs in any of our studies in rheumatoid arthritis, postpartum depression and migraine. This clinical data supports the risk analysis in accordance with the standard for risk management, ISO 14971:2019, that concludes that the risks related to the use of the Nesos System are low.

Aim 2: Biological Assessments

There are no physical risks associated with the non-invasive physiological recording procedures. These tests are commonly used in clinical and research settings.

For electroencephalogram (EEG), there may be some discomfort wearing the electrode cap; fortunately, only dry electrodes are used that require no gels to record a signal. Additionally, the size and tightness can be adjusted for each participant. The electrodes only record activity and do not produce any sensation.

For electrocardiogram (ECG), only four electrodes will be connected to the participant's body. There may be some discomfort or skin irritation at the sites of the electrode connections. However, this usually dissipates shortly after the electrodes are removed.

The non-invasive blood pressure (NIBP) system involves the use of a finger cuff to obtain a measurement. There may be some discomfort along the finger and wrist. However, this is remedied by properly adjusting the system to the comfort of the user.

The galvanic skin response (GSR) sensors involve placing 2 electrodes on the fingertips of the participant, assessing skin conductance by measuring the voltage difference between the two electrodes. As a result, there may be some discomfort to participants.

Protocol Number: 21-0640

February 1, 2022

There are no known risks for either the eye tracking device or respiratory belt. However, they may cause discomfort in some participants. The wearable eye tracker is a pair of clear, plastic glasses with unobtrusive design (no side or bottom frame) to provide a normal and maximal field of view. The respiratory belt is placed around the torso and can be adjusted to a comfortable setting for the participant.

Aim 2: Blood Draw

There are no major risks associated with the drawing of blood. However, blood draws may cause discomfort or bruising. In rare cases, it can also cause fainting or an infection at the site.

Treatment of this complication, if necessary, usually involves a warm compress to the area for one to several days. Only trained staff will draw blood. This study consists of 2 blood draws, and it is considered minimal risk since the study will only involve the collection of approximately 12mL of blood at baseline and follow-up. This is below the maximum blood collection volume generally deemed minimal risk for this study population (i.e., no more than 50 mL in an 8-week period, with no more than two draws occurring in any 7-day period).

2.3.2 KNOWN POTENTIAL BENEFITS

There is no direct benefit to the focus group participants. There is an indirect benefit to other Veterans whose access to these treatments in the future may be increased by this focus group participation.

The pilot clinical trial participants could potentially experience benefit in terms of a reduction in PTSD symptoms.

The results of the proposed project will have important implications for the next step in determining the effectiveness of taVNS as a potential treatment for individuals with PTSD. The pilot feasibility study is a first step toward bringing the latest advances in non-invasive, easy to use bio-electronic medicine technology to a population with high rates of PTSD who experience barriers to treatment engagement and adherence. Ultimately, the findings of the study can serve as a blueprint for the next stage of a large, randomized controlled trial research protocol, to assess the benefits of this novel and non-invasive approach to reduction of PTSD symptoms for WTC responders across sites. This could eventually be a successful approach to other responder populations in the United States and internationally.

3 OBJECTIVES AND ENDPOINTS

Aim 1:

Protocol Number: 21-0640

February 1, 2022

The primary objective:

To conduct a formative phase evaluation in order to ensure that the taVNS intervention and the pilot study methodology are **feasible** for use with 9/11 WTC responders with PTSD using a focus group of 10 WTC responders with elevated PTSD symptoms.

A secondary objective:

To conduct a formative phase evaluation in order to ensure that the taVNS intervention and the pilot study methodology are **relevant and acceptable** for use with 9/11 WTC responders with PTSD using a focus group of 10 WTC responders with elevated PTSD symptoms.

Primary Study Endpoint:

Feasibility

Secondary Study Endpoint:

Relevance and acceptability

Aim 2:

The primary objective:

To conduct a randomized, double blind placebo controlled parallel-design pilot study with 30 WTC responders affiliated with the WTC Health Program (WTCHP) who have PTSD to determine whether the taVNS intervention and efficacy study methodology are feasible for use with this population.

A secondary objective:

To conduct a randomized, double blind placebo controlled parallel-design pilot study with 30 WTC responders affiliated with the WTC Health Program (WTCHP) who have PTSD to determine whether the taVNS intervention and efficacy study methodology are acceptable for use with this population.

Primary Study Endpoint:

The primary endpoint of this study will be the feasibility of the taVNS intervention. This will be measured at the 8-week follow-up. Feasibility will be evaluated as: (1) rates of recruitment (per month), (2) adherence to the taVNS intervention, (3) 8-week retention, and (4) duration and completion rate of study assessments. Feasibility is defined as the ability to recruit 75% of eligible participants who were approached, as well as to show adherence to the intervention and retention rates of 70% each.

Secondary Study Endpoint:

Protocol Number: 21-0640

February 1, 2022

The secondary endpoint of this study will be acceptability of the taVNS intervention. This will be measured at the 8-week follow-up. Acceptability will be evaluated by assessing: (1) the time to completion of questionnaires, (2) percentage of missing data from questionnaires, (3) the time to completion of the biological data and blood draw, (4) the rate of refusal of biologic measurements and blood draw, and (5) the score on the taVNS Satisfaction and Usefulness Questionnaire.

Tertiary endpoints of this study include multiple mental health and biologic potential endpoints to be measured at the baseline of the pilot feasibility trial as well as at the 8-week follow-up time point. Tertiary outcome measures include potential taVNS endpoint measures. At the baseline and 8-week follow-up visits, validated self-report mental health measures, biological measures, and the CAPS PTSD interview (at screener and follow-up) will be administered. To examine potential mechanisms of action and any acute and longer-term change in these mechanisms, all biological measures will be administered at the baseline visit 10 minutes before using the device, and then again one time at the 8 week follow-up visit. These tertiary outcome measures and potential mechanisms of action will be used to inform the design of a future RCT to evaluate taVNS efficacy. We will assess measurement quality, amount of missingness/non-response, length of measurement collection, and costs. These measures will also be used to provide parameter estimates for power calculations for a future RCT.

We will also use the initial study results to understand signals that point to potential variables to include that best indicate taVNS efficacy, and potential mediators of the impact of taVNS on PTSD when implemented in a future RCT involving multiple WTCHP sites. As such, preliminary efficacy of taVNS on PTSD symptoms will be assessed.

Differences between baseline and post-treatment mental health measures will be used to generate hypotheses for a future larger RCT targeting PTSD symptoms as a primary outcome, and anxiety, depression, and sleep quality as secondary outcomes, in order to more robustly evaluate taVNS efficacy among a larger sample of WTC responders with PTSD thereby conferring greater statistical power. We will also use results from this pilot to generate hypotheses regarding potential mechanisms of action including the various inflammatory, neural and cardiovascular changes that correlate with treatment outcomes.

Blood will be drawn to assess markers of inflammation before using the device, and again at the 8-week follow-up visit. This allows us to collect data to understand potential acute and long term effects based on these preliminary efficacy results. These tertiary outcome measures and potential mechanisms of action will be used to inform the design of a future, RCT to evaluate taVNS efficacy. Measurement quality, amount of missingness or non-response, length of measurement collection, and costs will be also assessed. These measures will also be used to provide parameter estimates for power calculations for a future RCT.

4 STUDY DESIGN

4.1 OVERALL DESIGN

Aim 1 is a formative phase evaluation to ensure that the taVNS intervention and the pilot study methodology are relevant and acceptable for use with WTC responders with PTSD. As such, it is appropriate to use qualitative methods. This will entail the implementation of a focus group that is guided by a discussion guide. The discussion guide will be finalized by the research team prior to recruitment. It will include questions to understand the relevance, feasibility and acceptability of: (1) using a taVNS device generally, (2) using it as treatment for PTSD, (3) the implementation protocol of the device, (4) the pilot study protocol (including the methodology details, timing, and both self-report, clinical, and biological assessments), and (5) the appropriateness of outcome measures.

Aim 2 seeks to conduct a randomized, double-blind placebo-controlled parallel-design pilot study, to determine whether the taVNS intervention and study methodology are feasible and acceptable for use with WTC responders with PTSD. It is important that the design is double-blind and placebo-controlled in order to have the most appropriate control and to limit bias on the part of the participant and investigators. In addition, as this is a feasibility study, it is important to replicate the methodology that will eventually be used with a larger trial in order to truly assess whether the intervention and methodology are acceptable, feasible and efficacious.

4.2 SCIENTIFIC RATIONALE FOR STUDY DESIGN

Posttraumatic Stress Disorder (PTSD) remains the most prevalent mental health (MH) diagnosis for first responders involved with responding to the 9/11 World Trade Center (WTC) terrorist attacks, with rates of PTSD much higher than that of the general population. There are a number of evidence-based treatments (EBT) for PTSD, with the strongest evidence base for trauma focused therapies, which typically require that patients engage with the index trauma and the associated fears and cognitions. This can be particularly difficult for PTSD patients for whom avoidance is a key symptom. Although these treatments are well supported, they are less effective in military and veteran populations in particular. Additionally, high dropout rates are observed across treatments for PTSD, with some studies yielding dropout rates of over 30%. Given the high rates of PTSD and the lower uptake of effective PTSD treatment among responders, there is a clear need to provide brief, easily accessible treatments to WTC responders to alleviate PTSD symptoms. There is a growing body of literature to support the use of vagus nerve stimulation (VNS) to treat a number of different disorders with promising animal model research regarding the use of VNS to address some of the features of PTSD, specifically, due to the impact that VNS has on key areas of the brain that are associated with fear extinction and hyperarousal in particular. The current study aims to determine whether the use of a novel, safe, non-invasive form of VNS, transcutaneous auricular VNS (taVNS), would be acceptable and feasible for use with WTC responders who have PTSD, and whether the methodology involved

Protocol Number: 21-0640

February 1, 2022

with a larger randomized controlled trial (RCT) to test taVNS efficacy would be acceptable and feasible. As such, the current study involves conducting a formative phase evaluation in the context of a focus group with WTC responders with elevated PTSD symptoms, in order to tailor the taVNS intervention and the pilot study methodology so that it's relevant and acceptable for use. The taVNS intervention will then be piloted in a randomized, double-blind placebo controlled parallel-design study with 30 WTC responders affiliated with the WTC Health Program who have PTSD. Outcomes include taVNS intervention and study methodology feasibility and acceptability. In addition, differences between baseline and post-treatment MH measures will be used to generate hypotheses for a future larger RCT aimed at evaluating taVNS efficacy in PTSD symptom reduction among a larger sample of WTC responders with PTSD. We will also use results to generate hypotheses regarding potential mechanisms of action including the various inflammatory, neural and cardiovascular changes that correlate with treatment outcomes. This pilot feasibility study is a first step toward bringing the latest advances in non-invasive, easy to use bioelectronic medicine technology to a population with high rates of PTSD who experience barriers to treatment engagement and adherence.

4.3 JUSTIFICATION FOR STIMULATION METHOD

The stimulation method here is taVNS, an emerging noninvasive form of VNS. It delivers electrical stimulation to an easily accessible target that innervates the human ear and has allowed researchers to expand on the promising applications of VNS without surgical intervention.

Stimulation parameters to achieve the intended effect may vary between each tested individual. The impedance of the electrode-skin interface, placement of the electrode on the ear, and unique anatomy between individuals makes it arbitrary to set a choice of specific stimulation amplitude parameters. For example, a specific current may not be perceptive in one person but may be painful for another. By adjusting the level of stimulation amplitude per individual instead of a one-size-fits-all parameter, we can establish similar levels of activation of the auricular branch of the vagus nerve. The min/max current range that the patient may receive during this study is 1 mAmp - 2.6 mAmp. The sham arm participants will not receive any current.

The intensity will be established as a function of individual perceptual threshold. The stimulation current for taVNS sessions will be just below the minimum amount of current that elicits a perceived sensation of at the target site. To preserve bias between taVNS and sham data, all participants will be told that they may or may not feel any sensation at every test session.

4.4 END OF STUDY DEFINITION

Protocol Number: 21-0640

February 1, 2022

A participant is considered to have completed the study if he or she has completed all study tests and visits. If a study participant fails to complete all study tests and does not return for all visits, he or she will be considered lost to follow up. If a participant has an adverse event they will discontinued from the study. Anyone can choose to end their participation at any time.

The study is considered complete once the last participant completes their final study visit, and all identifiable data has been collected and analyzed.

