6 STUDY INTERVENTION

6.1 STUDY INTERVENTION(S) ADMINISTRATION

6.1.1 STUDY INTERVENTION DESCRIPTION

Aim 1: A Focus Group Discussion Guide will be finalized by the research team prior to recruitment (see Appendix 1 for example blank focus group data collection instrument). It will include questions to understand the relevance, feasibility and acceptability of: (1) using a taVNS device generally, (2) using it as treatment for PTSD, (3) the implementation protocol of the device, (4) the pilot study protocol (including the methodology details, timing, and both self-report, clinical, and biological assessments), and (5) the appropriateness of outcome measures. The estimated duration for the focus group is \approx 90 minutes. Drs. [name] and [name] will co-lead the focus group and the coordinator will take notes, write the minutes, and audio-record the session. [name] and/or [name] will demonstrate the device. Individuals will have the opportunity to handle the devices and there will be sanitizing wipes to be used in between. The focus group will be transcribed for qualitative analyses.

Aim 2:

Table 1. Aim 2 Outcome Measures	
Primary Outcome Measures (measured at 8 weeks)	
FEASIBILITY	
Recruitment	
-% responders who meet criteria 1-3 who accepted to come in for the CAPS interview (goal=33%)	
-% eligible responders who meet criteria 1-4 of those who came in for the CAPS interview (goal=66%)	
-% eligible responders who meet all criteria and were recruited and consented (goal = 75%)	
Retention	
-% participants who complete baseline and 8-wk measures (both survey and biological measures) (goal = 90%)	
Adherence	
-% participants who used taVNS 15 min/day once a day for 8 weeks (21 hours total) (goal=80%)	
Secondary Outcome Measures (measured at 8 weeks)	
ACCEPTABILITY	
Collection of Measures	
-Time (minutes) to fill out questionnaires (goal =<30 min)	
-Missing data from questionnaires: % items complete on the baseline and 8-wk self-report surveys (goal=90%)	
-Time (minutes) to collect biological data and blood draw (goal=10 min at baseline and 10 minutes at follow-up)	
-Rate of refusal of biologic measurements/blood draw (goal=5% refusal)	
Satisfaction	
-taVNS Intervention Study satisfaction survey (Adapted from Bakken et al.) (range=12-60; goal=100%-with score >47 among intervention group) ¹⁰⁰	
Tertiary Outcome Measures (measured at baseline and 8 week follow-up)	
Mental health symptoms (assessed to indicate signals for hypothesis generation)	

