7 STUDY DISCONTINUATION AND PARTICIPANT WITHDRAWAL

7.1 DISCONTINUATION OF STUDY INTERVENTION

Discontinuation of taVNS does not necessarily mean discontinuation from the study, as remaining study procedures may be completed as indicated by the study protocol. If a clinically significant finding is identified after enrollment, a qualified investigator will determine if any change in participant management is needed. Also, the participant may be notified of the finding and recommended to seek further clinical evaluation and care.

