7.2 PARTICIPANT DISCONTINUATION/WITHDRAWAL FROM THE STUDY

Given that participation in this study is voluntary, participants may elect to withdraw at any time by notifying a researcher. It is also possible that participation in this study may end without the participant's consent. This decision may be made by a researcher, the Northwell Health Human Research Protection Program, or a federal or state regulatory agency.

Reasons for withdrawal may include: failure to comply with study requirements; failure to keep study appointments; a change in their medical history, medications, or lifestyle (including alcohol, tobacco, or substance usage) that results in them no longer meeting study eligibility; inability to tolerate study procedures; it is not in the participant's best interest to continue on this study; or the study is stopped.

Participants that prematurely withdraw from the study due to an adverse event will be followed (e.g. telephone contact, follow-up visits, etc.) until resolution of the event or they indicate they no longer want to be contacted. In addition, a designated investigator will have access to treatment status at all times and provide that information to appropriate medical personnel in the event of medical emergencies. If the participant withdraws from this study or if s/he is withdrawn from the study, any data already collected will continue to be used, but no new data will be collected. The reason for participant discontinuation or withdrawal from the study will be recorded.

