8.3 ADVERSE EVENTS AND SERIOUS ADVERSE EVENTS

8.3.1 DEFINITION OF ADVERSE EVENTS (AE)

An adverse event is any untoward medical occurrence regardless of causality assessment. An adverse event can be an unfavorable and unintended sign, symptom, syndrome, or disease associated with or occurring during an investigation, whether or not considered related to the investigation.

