8.3.3 CLASSIFICATION OF AN ADVERSE EVENT

8.3.3.1 SEVERITY OF EVENT

Protocol Number: 21-0640

February 1, 2022

For consistency of labeling and categorizing adverse events, the Common Terminology Criteria for Adverse Events (CTCAE v4.03) will be used on this study. The grading will be performed as follows:

- Grade 1 = mild adverse event.
- Grade 2 = moderate adverse event.
- Grade 3 = severe and undesirable adverse event.
- Grade 4 = life-threatening or disabling adverse event.
- Grade 5 = death.

The identification of an adverse event may be from observation, participant notification, clinical assessment, or results from tests.

- **Mild** – Events that require minimal or no treatment and do not interfere with the participant's daily activities.
- **Moderate** – Events that result in a low level of inconvenience or concern. Moderate events may cause some interference with functioning.
- **Severe** – Events that interrupt a participant's usual daily activity and may require treatment. Severe events are usually potentially life-threatening or incapacitating.
- **Life-threatening** – Events that require urgent intervention to sustain life or prevent severely debilitating condition.
- **Death** – Events that are related to death.

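### Section 4.4 discontinues any participant who has an adverse event, so a mild or unrelated event known before week 8 becomes a failure on the primary retention endpoint, against the narrower rule in 2.3.1 and the discretion in 7.1 and 7.2

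*Protocol*

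**What the plan says.** Section 4.4 (End of Study Definition) says: "If a participant has an adverse event they will discontinued from the study". No severity, seriousness or causality condition is attached.

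Three other places determine what that sentence does:
- **Scope of an adverse event.** Section 8.3.1: "An adverse event is any untoward medical occurrence regardless of causality assessment". Section 8.3.3.1 includes a mild category: "Events that require minimal or no treatment and do not interfere".
- **Consequence of leaving.** Section 7.2, for a participant who withdraws or is withdrawn: "any data already collected will continue to be used, but no new data will be collected".
- **Endpoint.** Table 1 in 6.1.1 lists retention among the primary measures, as the percentage completing both baseline and 8-week measures, survey and biological, with a goal of 90%. Sections 3 and 8.1 set the feasibility threshold for retention at 70%.

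Two sections handle the same situation more narrowly:
- **Section 2.3.1:** "for participants with any severe or persistently worsening symptoms or adverse reactions, the taVNS therapy will be immediately discontinued", and "they will be removed from the study, considered treatment failures, and receive medical treatment as necessary".
- **Section 7.1:** "Discontinuation of taVNS does not necessarily mean discontinuation from the study, as remaining study procedures may be completed". It leaves clinically significant findings to a qualified investigator. Section 7.2 then lists reasons that may lead to withdrawal; simply having an adverse event is not among them.

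**The concern.** Retention is meant to show whether responders can be kept in an 8-week taVNS trial. Under 4.4 as worded it would partly measure how many people had any adverse event that staff learned of before week 8, including events unrelated to the device. Events can become known in that window: the coordinator phones at week 4, and participants may call at any time (10.1.6).

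The 70% threshold is part of the definition of feasibility, and 9.1 says the lower confidence limit will inform retention planning for the next RCT. Staff who follow 4.4 and staff who follow 2.3.1 could report different retention for the same participants. The 8-week clinical and biological measures would also be lost for those discontinued. That loss matters less, because the protocol uses those measures only to generate hypotheses and to give planning estimates that it says it will treat with caution.

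**Working it through.** **Inputs from the protocol.** N = 30 (9.3.1). Expected retention is 90% (9.1). The threshold is 70%, i.e. 0.70 × 30 = 21 participants (3, 8.1). Intervals are two-sided 95% Clopper-Pearson (9.1).

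**Assumed input.** The protocol gives no adverse event rate. Let q be the share of otherwise retained participants with any adverse event known before week 8, taken as 5, 10, 20 and 30%.

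**The plan's own figure.** The Clopper-Pearson lower limit is the 0.025 quantile of Beta(x, 30 − x + 1), with x = 30 × proportion. At 0.90, x = 27 and the interval is 0.735 to 0.979, as in Table 2 of section 9.2. The other five rows of that table also reproduce.

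**Effect of 4.4 followed literally.** Take 90% as retention without the rule, and events as independent of other dropout:
- Expected retention r = 0.90 × (1 − q).
- Additional participants not retained = 30 × 0.90 × q.
- Chance of meeting the threshold = P(Bin(30, r) ≥ 21).

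| q | r | Additional not retained | P(at least 21/30) | Lower limit at r |
|---|---|---|---|---|
| 0 | 0.900 | 0 | 0.9995 | 0.735 |
| 5% | 0.855 | 1.35 | 0.99 | 0.679 |
| 10% | 0.810 | 2.7 | 0.95 | 0.626 |
| 20% | 0.720 | 5.4 | 0.68 | 0.527 |
| 30% | 0.630 | 8.1 | 0.28 | 0.435 |

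**Break-even.** Expected retention falls below 70% once q exceeds 1 − 0.70/0.90 = 22.2%. In counts, starting from 27 of 30, six discontinuations under 4.4 leave 21/30 = 70%, and a seventh leaves 20/30 = 66.7%.

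**Sensitivity to independence.** Suppose people with events would be retained at only 60% without the rule, with overall retention still 90% and q = 20%. The rule then removes only the 0.20 × 0.60 = 0.12 who would have stayed. Retention is 0.90 − 0.12 = 0.78, and P(at least 21/30) is 0.90 rather than 0.68. The 60% is an assumption.

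**Sensitivity to the starting level.** Section 2.1 cites an average dropout of 18% in PTSD trials. With 82% as retention without the rule, P(at least 21/30) goes from 0.97 to 0.89, 0.76, 0.38 and 0.11 for the same q, and the break-even q is 1 − 0.70/0.82 = 14.6%. That figure is not specific to this device.

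**The case against.** The strongest reply is that 4.4 is one stray sentence in an end-of-study definition, and that the sections written for the purpose point the other way. Section 2.3.1 names the group to be removed, 7.1 gives an investigator the decision, and the reasons in 7.2 are discretionary. This stands as evidence of intent, and the narrower rule is probably what was meant. It does not remove the conflict: 4.4 is current text, it is unqualified, and no section says which rule governs.

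The size is also open to challenge. The protocol calls device side effects rare, and only one contact is scheduled between the baseline and 8-week visits, so many events may first surface at week 8. The 90% expectation, like the 82% alternative, may already include adverse-event withdrawals, in which case applying q on top counts some losses twice. All of this stands. Unrelated events over 8 weeks also fall under 4.4, so q is unknown rather than shown to be either small or large.

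It is fair, too, that attrition from adverse events is a proper part of retention if the removal rule will be carried into the larger trial. That supports counting removals under 2.3.1 as failures. It does not support counting a participant with a mild, unrelated event who was willing to continue.

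A reader might go further and infer that 2.3.1 and 7.1 contradict each other, or that the event follow-up in 8.3.4 contradicts 4.4. The text supports neither. Section 7.1 says only that stopping taVNS does not necessarily end participation, and 2.3.1 names a group for whom it does, so both can be followed. The tracking of events in 8.3.4 is compatible with earlier withdrawal, because 7.2 also follows people who withdraw because of an adverse event.

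**Conclusion.** The concern holds as a conflict of wording that reaches a primary endpoint. Section 4.4, read with 8.3.1, 8.3.3.1, 7.2 and Table 1, makes any adverse event known before week 8 a retention failure. Section 2.3.1 and the discretion in 7.1 and 7.2 do not.

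Confidence is high in the textual conflict and lower in its size, which is illustrative and rests on an assumed q, on 90% as the level without the rule, and on independence. On those terms the 70% decision is little affected at q of 5% or less, is still met with probability 0.95 at 10%, and becomes doubtful from about 20%. The effect shrinks if 90% already includes adverse-event withdrawals or if people with events would have dropped out anyway. The documents do not support the inference that the trial is likely to miss its threshold.

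**What to change.** Delete the sentence in 4.4, or replace it with wording to this effect: an adverse event alone does not end participation; the device is stopped and the participant removed only under the 2.3.1 criterion or a 7.2 withdrawal decision; all other participants stay in follow-up and are asked to complete the 8-week measures.

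Leave the removal rule in 2.3.1 as it is, since it is a coherent safety decision. Leave the data stop in 7.2 as it is, since it also covers withdrawals imposed by the oversight bodies and the pregnancy withdrawals in 8.3.7.

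The cost is one sentence. The 8-week visits it preserves are already planned within the 30 participants.

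A minor correction at the same time: the retention definition in 9.3.1 refers to 6-week measures and should read 8-week, as Table 1 does.
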